## Continuous Secondary Efficacy Endpoints

Change from baseline in 9 point modified Mayo score or total Mayo score at Week 8 will be summarized in each treatment group and overall. Descriptive statistics will be presented. An analysis of covariance (ANCOVA) model will be used to evaluate whether the means of change from baseline are equal across treatment groups, while statistically controlling for the effects of baseline value and previous exposure to anti-TNF $\alpha$  treatment/other biological treatments. The model will include treatment group, baseline value, with/without previous exposure to anti-TNF $\alpha$  treatment/biological treatment as main effects. Least square mean (LS Mean) and 90% CI for each treatment group will be provided at Week 8.

---

Document:

\\\ieedc-vnasc01\Biosdata\Reistone\SHR0302\CZA55021\Biostatistics

Author:

[REDACTED]

Version Number:

Final v1.2

Version Date:

23Mar2021

[figure not shown]
Template No: CS\_TP\_BS016 Revision 5  
Effective Date: 01Apr2018

Reference: CS\_WI\_BS005

A partial Mayo score is the Mayo score without endoscopy component. Hence the maximum is 9 points and minimum 0 point. A partial Mayo score will be assessed at baseline, Week 1, Week 4, Week 8, Week 9, Week 12, Week 16, Week 18, early withdrawal visit and follow up visit, as secondary endpoints.

Changes from baseline in partial Mayo score at Weeks 1, 4, 8, 9, 12 and 16 will be summarized descriptively. For each visit, the change from baseline in partial Mayo score will be calculated. For the change from baseline value at each visit, ANCOVA model including treatment group, baseline value, with/without previous exposure to anti-TNF $\alpha$  treatment as main effects will be used to assess the treatment effect in partial Mayo score. LS Mean and 90% CI for each treatment group will be provided at Week 1, 4, and 8.

A figure will be used to present mean and 90% CI of the partial Mayo score at each visit in each treatment group.

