5.2 Inclusion Criteria

Subjects must meet all of the following inclusion criteria to be eligible for enrolment into the study;

1. Male and Female subject age ≥ 18 and ≤ 75 years of age at randomization.
2. Active ulcerative colitis with a 9-point modified Mayo score of 5 to 9 points and endoscopic subscore of 2 to 3 (The duration of the time between endoscopy and baseline should not exceed 10 days and allow central over read turn over before randomization).
3. Subject should have at least three-month history of Ulcerative Colitis diagnosis at randomization.
4. Subjects deemed by the treating physician as having inadequate response, loss of response or intolerance to the conventional treatment (oral 5-ASA, immune-suppressants or corticosteroids), or previously exposed to anti-TNF therapy (e.g. infliximab, adalimumab) or other biological treatment (e.g. Vedolizumab) having discontinued the treatment for:
 - Infliximab: a minimum of 8 weeks prior to baseline
 - Adalimumab: a minimum of 10 weeks prior to baseline
 - Ustekinumab: a minimum of 14 weeks prior to baseline
 - Vedolizumab: a minimum of 17 weeks prior to baseline
 - For the other biological treatments, they should discontinue for a minimum of 5 half-lives prior to baseline.
5. If subjects are currently receiving the following treatment for UC, they are eligible for the study, provided they are on stable dose for the required period of time:
 - Oral 5 ASA or Sulfasalazine, stable dose for at least 2 weeks prior to baseline and during the study treatment period.

AND/OR

- Oral corticosteroids (prednisolone \leq 30mg/day or less or equivalent) stable dose for at least 2 weeks prior to baseline. This is not applicable to the subjects who have only exposed to 5-ASA previously as per inclusion criteria 4.

6. Subject must have no evidence of active, latent, or inadequately treated infection with *Mycobacterium tuberculosis* (i.e., tuberculosis [TB]), as defined by the following:

- A negative Mantoux Purified Protein Derivative (PPD) skin test result (\leq 5 mm of induration), or negative QuantiFERON TB Gold (QFT Gold test) /or T-Spot test performed within the 3 months prior to/within screening;

AND

- Subject must have a chest radiograph, taken within the 3 months prior to/within screening, and showing no changes suggestive of active TB infection.

AND

- Subject must have no history of either untreated or inadequately treated latent or active TB infection

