6.2 Treatment Assignment

Subjects will be randomized into the trial in a 1:1:1:1 allocation ratio to SHR0302 8mg QD, placebo, SHR0302 4mg QD or SHR0302 4mg BD for the treatment phase provided they have satisfied all inclusion/exclusion criteria. Subjects will be stratified according to whether or not they have had previous exposure to anti-TNF α /biological treatment and randomized at baseline according to a computer generated pseudo random code using the method of permuted blocks balanced within each randomization strata. Subjects randomized into placebo in treatment phase will also have a pre-assigned randomized treatment sequence for extension phase, which are 3 active groups (placebo -> 4mg QD, placebo -> 4mg BD, and placebo -> 8mg QD) in a 1:1:1 ratio. Subjects randomized to the active arms for treatment phase will remain in the same dose group in the extension phase.

After the completion of treatment phase, subject may choose to enroll into the extension phase according to the group they were randomized to for the extension phase. All the subjects that have completed the first treatment phase have the option not entering into the extension phase after first 8 weeks of treatment. Early withdrawn subjects during the first treatment phase cannot enter the extension phase.

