9.3.4.3 Efficacy Analysis

Analysis of the Primary Efficacy Endpoint

The primary analysis will be based on the FAS population. In addition, an analysis of the PPS population will be used to support the primary efficacy analysis.

For clinical response at week 8, the comparisons of the percentage of subjects achieving clinical response in each treatment versus placebo will be made using a stratified Cochran-Mantel-Haenszel (CMH) test with stratification according to prior anti- TNF α /biological treatment (with or without). Missing data will be imputed as Non-completers considered failure (NCF).

Sensitivity analyses for the primary endpoint include: (1) the same analysis using the per-protocol analysis set (2) using last-observation-carried-forward (LOCF) imputation for subscore other than endoscopy of Mayo score.

Analysis of the Secondary Efficacy Endpoints

Dichotomized secondary efficacy endpoints listed below will be analyzed by using a CMH Chi-Square test with stratification according to prior anti- TNF α treatment (with or without). Missing data will be imputed as Non-completers considered failure (NCF).

- ✓ The percentage of subjects with clinical remission (per 9-point modified Mayo score) at week 8
- ✓ The percentage of subjects with clinical remission (per total Mayo score) at week 8
- ✓ The percentage of subjects achieve endoscopic remission at week 8

The continuous secondary endpoints listed below will be analyzed using an analysis of covariance (ANCOVA) model including treatment group, baseline value, with/without previous exposure to anti-TNF α treatment as main effects. Missing data will be imputed by using Last-observation-carried-forward (LOCF) approach for subscore other than endoscopy of Mayo score.

- ✓ Change from baseline in 9-point modified Mayo score at week 8
- ✓ Change from baseline in total Mayo score at week 8
- ✓ Changes from baseline in partial Mayo score (Mayo score without endoscopy) at week 1, 4, 8, 9, 12 and 16.
- ✓ Change from baseline in the level of biomarkers CRP, fecal calprotectin.

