Reference: CS\_WI\_BS005

phase after first 8 weeks of treatment. All patients in the extension phase are followed-up for further 2 weeks until week 18. Patients who have completed the first 8-week of treatment phase, but decided not entering into extension phase are required to attend the 2-week follow-up visit. Early withdrawn patients during the first 8-week treatment phase cannot enter the extension phase. Early withdrawal visit should be done within 2 weeks after last dose/decision of withdrawal. The total duration of the study participation, including extension and follow-up, will be approximately 18 weeks.

At the baseline visit, patients with moderate-to-severe active ulcerative colitis, with a modified 9-point Mayo score of 5 to 9 points and endoscopic subscore of 2 to 3, and fulfilling all the inclusion/exclusion criteria will be randomized into one of the four treatment arms for the treatment phase: 4mg QD, 8mg QD, 4mg BD of SHR0302 or placebo. All the patients will be stratified according to whether they have previously exposed to anti-TNF $\alpha$ /biological treatment. Patients randomized into placebo in treatment phase will also have a pre-assigned randomized treatment sequence for extension phase, which are 3 active groups (placebo -> 4mg QD, placebo -> 4mg BD, and placebo -> 8mg QD) in a 1:1:1 ratio. Patients randomized to the active arms for treatment phase will remain in the same dose group in the extension phase.

Primary endpoint assessment will be conducted at week 8. 9-point modified Mayo score is the Mayo score excluding physician global assessment (PGA) subscore. 9-point modified Mayo score will be collected as the primary endpoint. This has been advised by the US FDA according to FDA guidance on ulcerative colitis trial. At the completion of the first 8-week treatment period, all patients, responders or non-responders, have the option to enter a blinded active arms 8-week extension phase according to the group they were randomized to for the extension phase. The end-of-study is defined as the date of the last patient's last visit or the actual date of follow-up visit/contact, whichever is later. The study design diagram is provided in below figure (Figure 1).

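### The SAP's partial Mayo ANCOVA, and the protocol's only model for CRP and fecal calprotectin, name anti-TNFα exposure alone, while randomisation was stratified on anti-TNFα/biological exposure

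*SAP*

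**What the plan says.** **Randomisation.** Protocol 6.2 states: "Subjects will be stratified according to whether or not they have had previous exposure to anti-TNF"α/"biological treatment and randomized at baseline according to a computer generated pseudo random code using the method of permuted blocks". SAP 3.1 repeats the factor: "All the patients will be stratified according to whether they have previously exposed to anti-TNF"α/biological treatment.

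**Eligibility.** Inclusion criterion 4 (protocol 5.2) admits patients "previously exposed to anti-TNF therapy (e.g. infliximab, adalimumab) or other biological treatment (e.g. Vedolizumab) having discontinued the treatment for" a listed minimum period. The list has separate entries for ustekinumab and vedolizumab.

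**Protocol 9.3.4.3.** The primary CMH test is stratified on anti-TNFα/biological treatment. The dichotomised secondary endpoints "will be analyzed by using a CMH Chi-Square test with stratification according to prior anti"-TNFα treatment only. The ANCOVA for the continuous secondary endpoints, including CRP and fecal calprotectin, contains "treatment group, baseline value, with/without previous exposure to anti-TNF"α treatment only.

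**SAP 15.1.1 and 15.2.1.** The primary CMH test and the adjusted differences for both remission endpoints and endoscopic remission use anti-TNFα/biological treatment. So does the ANCOVA for the 9-point and total Mayo scores: "treatment/other biological treatments. The model will include treatment group, baseline value, with/without previous exposure to anti-TNF"α treatment/biological treatment. Two paragraphs later the partial Mayo model is given as an "ANCOVA model including treatment group, baseline value, with/without previous exposure to anti-TNF"α treatment, and the description of the factor ends there.

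**The concern.** The two factors are not the same variable. A patient whose only biological was vedolizumab or ustekinumab belongs to the exposed randomisation stratum but has had no anti-TNF. A programmer who follows the partial Mayo sentence as written would code that patient as unexposed.

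The usual principle is to analyse by the factor used to randomise, so that the model reflects the design and the standard error takes credit for the stratification. At stake are a little precision and the comparability of partial Mayo with the other Mayo-based results. There is also a documentation gap. The SAP departs from the protocol's covariate for some secondary endpoints and keeps it for one, and SAP 3.3, which lists changes from the protocol, mentions neither. A reader cannot tell a decision from an omission.

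**Working it through.** **Step 1: the texts side by side.**

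| Place | Use | Exposure factor named |
|---|---|---|
| Protocol 4.2 and 6.2; SAP 3.1 | Randomisation strata | anti-TNFα/biological |
| Protocol 9.3.4.3; SAP 15.1.1 | Primary CMH | anti-TNFα/biological |
| Protocol 9.3.4.3 | CMH, three dichotomised secondary endpoints | anti-TNFα only |
| SAP 15.2.1 | Same three endpoints | anti-TNFα/biological |
| Protocol 9.3.4.3 | ANCOVA, all continuous secondary endpoints | anti-TNFα only |
| SAP 15.2.1 | ANCOVA, 9-point and total Mayo | anti-TNFα/biological |
| SAP 15.2.1 | ANCOVA, partial Mayo | anti-TNFα only |
| SAP 15.2 | CRP, fecal calprotectin | not listed; no model |

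Within the SAP, one model carries the narrower factor. Across both documents, CRP and fecal calprotectin carry it too, because the protocol sentence is the only model they have.

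**Step 2: does the plan's own arithmetic depend on this?** The plan states 80% global power with 35 evaluable patients per arm, and 152 randomised. A simulation of 400,000 trials used response rates of 0.57, 0.57 and 0.50 against a shared placebo arm at 0.30, pooled two-sided tests, and Hochberg at 0.10. It gives 80.0%. For the total, 140/0.92 = 152.2, which the plan gives as 152. The calculation concerns the primary endpoint and contains no covariate, so the wording at issue changes neither figure.

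**Step 3: size of the effect on an ANCOVA.** The documents give none of the inputs needed, so the following are assumptions:
- residual standard deviation σ = 2 points;
- share with anti-TNF exposure q_T = 0.25;
- share exposed only to another biological q_O = 0 to 0.10;
- outcome difference between the randomisation strata β = 0.5 to 1.0 point.

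Among patients coded unexposed on the narrow factor, the share who belong to the exposed stratum is q = q_O/(1 − q_T). The residual variance becomes σ² + β² q(1 − q)(1 − q_T). The standard error is multiplied by the square root of that quantity divided by σ².

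Worked case, q_O = 0.10 and β = 1:
- q = 0.10/0.75 = 0.133
- added variance = 1 × 0.133 × 0.867 × 0.75 = 0.087
- √(4.087/4) = 1.011, a rise of about 1.1%

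| q_O | Patients of 152 | SE rise, β = 0.5 | SE rise, β = 1.0 |
|---|---|---|---|
| 0 | 0 | 0% | 0% |
| 0.02 | 3.0 | 0.06% | 0.24% |
| 0.05 | 7.6 | 0.15% | 0.58% |
| 0.10 | 15.2 | 0.27% | 1.08% |

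**The case against.** The strongest reply is that this is shorthand. The SAP defines no separate anti-TNF-only variable. Its subgroup list (7.3), disposition table (9) and baseline characteristics (10) all use the combined factor, and the preceding model in the same subsection names both exposures. On that view the programmer would use the combined variable and nobody would be miscoded. This is plausible, and it makes the miscoding conditional on a literal reading. It does not remove the need to correct the sentence: the full factor has just been written out, so a shorter term invites the question whether a different one is meant.

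A second reply is that the SAP already restores the full factor for the other Mayo-based secondary endpoints. That stands. For those endpoints, what remains is only that SAP 3.3 does not record the change.

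A third is that the stakes are low. That also stands. Partial Mayo is a secondary endpoint outside the Hochberg procedure, and the SAP reports its least-squares means only at Weeks 1, 4 and 8.

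**Conclusion.** The inconsistency is in the current text of both documents and is worth correcting, but it is minor. On the assumptions shown, the cost is a standard error larger by 0 to about 1.1%, plus a loss of consistency between endpoints. That range rests on an assumed share of patients, stratum effect and standard deviation.

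Three stronger readings are not supported:
- A reader might infer that the balance from stratified randomisation is lost. Balance is fixed at allocation, and a covariate in one model cannot undo it.
- A reader might infer that partial Mayo is the sole exception. The protocol's CRP and fecal calprotectin ANCOVA has the same wording.
- A reader might infer that a known number of patients will be miscoded. The documents do not say how many had only a non-anti-TNF biological, and miscoding follows only if the sentence is programmed literally.

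The primary analysis, the 152 patients and the 80% power are not touched.

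**What to change.** - In SAP 15.2.1, define the exposure term in the partial Mayo ANCOVA as the randomisation stratum: previous anti-TNFα/biological exposure, yes or no.
- Specify the same term for the CRP and fecal calprotectin ANCOVA, which the SAP does not currently describe.
- Either align the secondary-endpoint text of protocol 9.3.4.3 with the stratum, or add one line to SAP 3.3 recording that the SAP uses the randomisation stratum where the protocol names anti-TNFα exposure only.

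The cost is a few words. No new data are needed, because the combined variable already serves the subgroup, disposition and baseline outputs. The wording should be settled before treatment codes are applied, so that the choice of covariate cannot appear to follow the results.

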### 15.2.2 Missing Data for Secondary Efficacy Endpoints

For dichotomized endpoints, missing data will be imputed as non-completers considered failure; if a patient is missing one or more Mayo subscores at the visit where the endpoint is being assessed, the patient would be considered a treatment failure.

For continuous endpoints, missing data will be imputed by using LOCF approach for results other than endoscopy of Mayo score. For missing endoscopy subscore, BOCF approach will be used.

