9.1 Hypothesis

The primary objective of the study will be evaluated for SHR0302 dose groups (8mg QD, 4mg BD, 4mg QD) compared to placebo group with respect to the percentage of patients with clinical response at week 8.

The Hochberg method will be used to maintain the 2-sided study-wise Type I error rate at 0.1. The null and alternative hypothesis for the primary endpoint that will be tested are:

H_{01} : The percentage of patients with clinical response at week 8 in SHR0302 8mg group – the percentage of patients with clinical response at week 8 in placebo group = 0;

H_{11} : The percentage of patients with clinical response at week 8 in SHR0302 8mg group – the percentage of patients with clinical response at week 8 in placebo group $\neq 0$.

H_{02} : The percentage of patients with clinical response at week 8 in SHR0302 4mg BD group – the percentage of patients with clinical response at week 8 in placebo group = 0;

H_{12} : The percentage of patients with clinical response at week 8 in SHR0302 4mg BD group – the percentage of patients with clinical response at week 8 in placebo group $\neq 0$.

H_{03} : The percentage of patients with clinical response at week 8 in SHR0302 4mg QD group – the percentage of patients with clinical response at week 8 in placebo group = 0;

H_{13} : The percentage of patients with clinical response at week 8 in SHR0302 4mg QD group – the percentage of patients with clinical response at week 8 in placebo group $\neq 0$.

Two-sided p-values for the treatment group differences will be provided for all comparisons by using CMH test. Thus, 3 p-values will be gained and start with the least significant comparison and continue as long as tests are not significant until the first time when a significant comparison occurs and all remaining hypotheses will be rejected. Order the three p values as $(p_{(3)}, p_{(2)}, p_{(1)})$, where $p_{(3)} \geq p_{(2)} \geq p_{(1)}$. The decision rules are provided in below figure ([Figure 2](#)).

[figure not shown]

Figure 2. The decision rules of hypothesis

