9.2 Study Design Considerations

9.2.1 Sample Size Assumptions

The sample size calculation is based on pairwise comparison of clinical response at week 8 among SHR0302 8mg, 4mg QD, 4mg BD dose group and placebo group at the 2-sided 0.1 significance level. 57%, 57%, 50%, 30% clinical response are assumed for 8mg QD, 4mg BD and 4mg QD dose group, placebo group at week 8 respectively. The planned sample size of 35 evaluable subjects per treatment group will provide 80% global power to detect at least 1 dose

group is different from placebo group by using Hochberg's step up test. The total sample size is 152 randomized subjects with consideration of 8% drop out rate.

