9.3.4.2 Missing Data

Binary data: Non-completers considered failure (NCF) will be used.

Continuous data: Last-observation-carried-forward (LOCF) approach will be used

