## 6.6 STATISTICAL TESTS

The default significant level will be 2-sided 0.1; confidence intervals (CI) will be 90% and

Document:

\leedc-vnasc01\Biosdata\Reistone\SHR0302\CZA55021\Biostatistics

Author:

[REDACTED]

Version Number:

Final v1.2

Version Date:

23Mar2021

Template No: CS\_TP\_BS016 Revision 5  
Effective Date: 01Apr2018

Reference: CS\_WI\_BS005

statistical tests will be two-sided, unless otherwise specified in the description of the analyses.

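### Partial Mayo change at Weeks 1, 4 and 8 rests on visit-by-visit ANCOVA with LOCF alone; a repeated-measures model on data already collected would be a cheap improvement

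*SAP*

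**What the plan says.** Partial Mayo is the Mayo score without endoscopy. In the placebo-controlled phase it is scored at baseline and Weeks 1, 4 and 8 (Protocol 5.12, Table 1).

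- **Model.** SAP 15.2.1 fits an ANCOVA to change from baseline at each visit, with treatment, baseline value and prior anti-TNFα exposure as terms: "LS Mean and 90% CI for each treatment group will be provided at Week 1, 4, and 8". Protocol 9.3.4.3 lists the same model, also for Weeks 9, 12 and 16.
- **Missing data.** SAP 15.2.2: "missing data will be imputed by using LOCF approach for results other than endoscopy of Mayo score". Protocol 9.3.4.2 agrees: "Continuous data: Last-observation-carried-forward (LOCF) approach will be used". The SAP's baseline-carried-forward rule covers only the endoscopy subscore, which partial Mayo does not contain, so LOCF is the only imputation here.
- **Alternatives.** The sensitivity analyses in SAP 15.1.2 and Protocol 9.3.4.3 are for the primary endpoint. SAP 7.2 generally leaves descriptive statistics unimputed, so observed-data summaries may appear, but they give no adjusted comparison with placebo.
- **Status.** "The default significant level will be 2-sided 0.1" (SAP 6.6). The Hochberg procedure in Protocol 9.1 covers the three primary comparisons; partial Mayo lies outside it.

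**The concern.** A patient last scored at Week 1 can enter the Week 8 ANCOVA with that Week 1 score, treated as if observed at Week 8. If scores in that arm go on changing between Weeks 1 and 8, the arm's Week 8 mean is pulled toward its early value. The pull grows with the number of patients who leave and with the change still to come. The dose-placebo difference therefore moves unless the pull is equal in both arms.

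Unequal loss is possible under this protocol. Some withdrawals follow safety rules (Protocol 5.6, 5.8 and 5.9), which may fall more on drug. Others follow insufficient response, which may fall more on placebo. SAP 3.3 confirms that some patients lack Week 8 primary efficacy results, without giving the number or the arm.

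At stake is the Week 8 estimate for the only Mayo outcome measured repeatedly in the controlled phase. The repeated scores that a better method needs are already collected.

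**Working it through.** **1. The plan's own figures.** The documents give no power, effect size or SD for partial Mayo. The primary-endpoint figures supply the arm size and the dropout rate.
- Protocol 9.2.1 assumes Week 8 response rates of 57% on 8 mg QD, 57% on 4 mg BD, 50% on 4 mg QD and 30% on placebo, and states: "The planned sample size of 35 evaluable subjects per treatment group will provide 80% global power". With a shared placebo arm, two-sided 0.10, pooled tests and Hochberg, 400,000 simulated trials give 80.1% power. This reproduces.
- "The total sample size is 152 randomized subjects with consideration of 8% drop out rate": 140 / 0.92 = 152.2, which agrees. 152 / 4 = 38 per arm, and 0.08 × 38 ≈ 3 patients lost per arm. No split by arm is given.

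**2. Closed form (dropout unrelated to score).** Shift in an arm = Σ d_k × (μ_k − μ_W8), where d_k is the fraction last seen at visit k and μ_k is the mean change at that visit.

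Assumed mean changes at Weeks 1/4/8: drug −1.0/−2.3/−3.0, placebo −0.6/−1.2/−1.5, so the true Week 8 difference is −1.5. Assumed last visit among leavers: 20% baseline, 30% Week 1, 50% Week 4.
- 8% in each arm. Drug: 0.016 × 3.0 + 0.024 × 2.0 + 0.040 × 0.7 = 0.124. Placebo: 0.016 × 1.5 + 0.024 × 0.9 + 0.040 × 0.3 = 0.058. Net +0.066, toward no effect.
- 20% drug, 4% placebo: 0.310 − 0.029 = +0.281.
- 4% drug, 20% placebo: 0.062 − 0.144 = −0.082, in favour of drug.
- Scores flat after Week 1 (assumed −1.5 drug, −1.0 placebo): +0.008 at 8%/8%, and +0.052 at 20%/4%, the largest of the cases tried.

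**3. Simulation with the same means.** 38 per arm, assumed score SD 2.2, dropout after Week 1 or 4 more likely in non-improvers, 4,000 trials per row. The likelihood column is a missing-at-random estimate of the kind a mixed model targets. Shift is LOCF minus the full-data estimate.

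| Dropout drug/placebo | LOCF | Likelihood | LOCF shift | SE | Shift/SE |
|---|---|---|---|---|---|
| 8%/8% | −1.45 | −1.50 | +0.05 | 0.50 | 0.11 |
| 4%/12% | −1.57 | −1.50 | −0.07 | 0.49 | 0.14 |
| 12%/4% | −1.33 | −1.51 | +0.18 | 0.50 | 0.35 |
| 4%/20% | −1.66 | −1.50 | −0.16 | 0.50 | 0.31 |
| 20%/4% | −1.18 | −1.49 | +0.31 | 0.51 | 0.61 |

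The likelihood estimate stays within 0.005 of the full-data value throughout.

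With no drug effect (both arms on the placebo trajectory) the LOCF shift is 0.00 at 8%/8%, −0.18 at 4%/20% and +0.18 at 20%/4%. The rejection rates at nominal 0.10 are 0.089, 0.116 and 0.127.

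**4. A second assumed trajectory.** Drug −0.9/−2.4/−3.4, placebo −0.6/−1.3/−1.7, SD 1.6/2.2/2.5, correlations 0.5 to 0.7, true difference −1.70, SE 0.59 for both methods.
- 8%/8%: LOCF −1.63 against −1.71 for likelihood; a repeat gave −1.61 against −1.69. The gap is 0.08, and 0.08 / 0.59 = 0.14 SE. The nominal 90% interval covers 90.3%.
- About 15% drug, 5% placebo: LOCF −1.46 against −1.70; a repeat gave −1.46 against −1.69. The gap is 0.23 to 0.24, and 0.24 / 0.59 = 0.41 SE. Coverage is about 86%.

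**The case against.** **The size is not in the documents.** This stands. The only planned dropout is 8% overall, and if it falls equally LOCF performs close to nominally. A reader might infer from the 15%/5% case that the plan understates the effect by 14% (0.24 / 1.70) with 86% coverage. Those figures rest on an assumed split and an assumed trajectory.

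**Bias depends on the estimand.** Both simulations take as truth the effect had everyone stayed on treatment, and they generate dropout at random given observed scores. That suits the likelihood model. If patients who leave lose the drug effect, the target in the second trajectory at 15% is −1.70 × 0.85 = −1.45, and LOCF's −1.46 is almost exact. This partly stands, because the plan does not say which effect it wants. It does not rescue LOCF in general. At 4% drug/20% placebo in the first trajectory that target is −1.5 × 0.96 = −1.44; LOCF gives −1.66 and the likelihood estimate −1.50. With no drug effect the target is zero under either definition, and LOCF still moves by 0.18 at 20%/4% or 4%/20%.

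**An early-withdrawal score exists.** Protocol 5.8 asks for partial Mayo at that visit if feasible, and SAP 15.2.1 lists the visit. A patient leaving after Week 1 need not carry a Week 1 score. This stands. However, neither document says whether the withdrawal score is the value carried, or whether baseline is carried when Week 1 is missing.

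**The plan is prespecified and consistent.** Protocol and SAP agree on LOCF, so there is no contradiction. The point is about a better method, not an error of drafting.

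**Conclusion.** The point holds as an optional improvement. LOCF is the only imputation behind the planned comparison of partial Mayo change, and no alternative comparison is planned. Under assumed trajectories the Week 8 difference shifts by about 0.05 to 0.08 points (0.11 to 0.14 SE) at 8% per arm. At 15-20% dropout on drug and 4-5% on placebo the shift is about 0.2 to 0.3 points (0.4 to 0.6 SE). It is near zero if scores are flat after dropout. The sign can favour drug or placebo, so LOCF is not conservative.

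Two stronger readings are not supported. One is that the trial's main conclusion is affected: the primary analysis counts non-completers as failures and is untouched. The other is that dose selection is compromised: SAP 3.1 bases it on efficacy, safety, tolerability and anti-inflammatory data together, and in dose-to-dose contrasts the shifts largely cancel if the doses have similar trajectories and dropout.

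**What to change.** In SAP 15.2.1 and 15.2.2, analyse partial Mayo change at Weeks 1, 4 and 8 with a mixed model for repeated measures on observed data. Include treatment, visit, treatment-by-visit, baseline, baseline-by-visit and the prior anti-TNFα/biologic randomisation stratum, with unstructured covariance. Keep the LOCF ANCOVA as a supporting analysis. State whether the early-withdrawal score is the value carried, and whether baseline is carried when Week 1 is missing.

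The cost is SAP wording, an entry among the changes from protocol in SAP 3.3, and one standard model; no new data are needed. The simulations show no gain or loss in precision (SE 0.59 either way in the second trajectory).

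The downside is that the model assumes missing at random and estimates the effect as if patients had stayed on treatment, which the SAP should say. The retained LOCF result shows only whether the answer depends on the method. It does not test that assumption, since the two methods differ in the simulations even where missing at random is true.
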